3.2. Randomisation

Participating PCPs were randomised to the intervention or to the control group. The unit of allocation is the PCP. This means that all physicians in the same practice were allocated to the same intervention and that either all or no physicians in the PCP were included in the trial. All patients cared for by the same primary care practice were exposed to the same intervention. We recruited 288 physicians on 01/12/2017 of which 8 physicians dropped out before including patients. The 280 physicians were distributed across 72 PCPs. We stratified the randomisation according to the laboratory with which they collaborated (3 strata). The level of confidence in using a CPOE was associated with the laboratory with which the PCP collaborated. This also assured that all PCPs collaborating with a laboratory were evenly distributed across both arms. Randomisation was done using a random numbers generator by the trial chief statistician. The research team will remain blinded to the allocation until after database lock. Further details on the randomisation scheme can be found in the protocol under 8.3.

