## 8.3 The randomisation scheme

PCP's will be randomized to either the intervention or control arm after stratification based on their experience in the use of a CPOE. We suspect that previous experience in using a CPOE will influence the effectiveness of order sets. Hence we will stratify all PCPs according to the self-reported experience in the use of a CPOE by its physicians. A random numbers generator will be used to randomise enrolled physicians. The research facility will be blinded to the randomization.

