## 8.6 Baseline data

Baseline data to compare participating physicians will be obtained at the start of the study. This data includes:

- Size of the PCP (how many active physicians)
- Age of the participating physician at the start of the study
- Sex of the participating physician
- Number of active years in general practice of the participating physician at the start of the study
- Average number of tests per laboratory order in the three months prior to the study, as a measure of baseline testing volume
- Experience in the use of a CPOE prior to the study

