### 9.3.2 Primary outcome analysis

To assess differences between the allocated groups in the proportion appropriate tests, a logistic GEE model will be used: of interest are the marginal proportions, not the individual probabilities of test to be appropriate.

The logistic GEE model will include the allocated group as a factor and patients as the clustering variable. The effect of the intervention will be expressed as the difference in proportions and will be presented together with its associated 95% confidence interval. The proportion of appropriate tests in the two allocated groups will also be estimated from the GEE model and presented with their 95% confidence intervals.

Appropriateness for the composite of all study tests will be compared between intervention and control groups groups. Furthermore, an analysis will be performed that only includes patients who have no indications in addition to the 17 study indications. This additional analysis will correct for an overestimation of inappropriate tests when more than one indication is selected, including indications not under evaluation. These tests would be considered inappropriate even though they could be appropriate according to one of the other indications not being evaluated.

The analyses will be performed on all patients from all physicians according to their allocated group.

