10.2. Analysis methods

10.2.1. Primary outcome analysis

Appropriateness

For the definition of the primary outcome, three numbers are relevant: (a) the number of requested tests which are appropriate, (b) the number of requested tests which are inappropriate and (c) the number of inappropriately not-requested tests. As indicated in section 5b, the latter number is only relevant for diabetes mellitus, chronic kidney disease, rheumatoid arthritis and thyroid disease. Per patient, aggregated over panels if multiple panels are available, the primary outcome is defined by the ratio $(a)/(a+b+c)$. We will refer to this ratio as the proportion of appropriate tests in the remainder.

To assess differences between the allocated groups in the proportion appropriate tests, a logistic generalized estimating equation (GEE) model will be used: of interest are the marginal proportions, not the proportions on patient, physician or PCP level.

The logistic GEE model will include the allocated group and laboratory as factors and PCP as the clustering variable. The effect of the intervention will be expressed as the difference in proportions and will be presented together with its associated 95% confidence interval. The proportion of appropriate tests in the two allocated groups will also be estimated from the GEE model and presented with their 95% confidence intervals.

Appropriateness for the composite of all study tests will be compared between intervention and control groups. Furthermore, an additional analysis will be performed that only includes patients who have no indications in addition to the 17 study indications. This additional analysis will correct for an overestimation of inappropriate tests when more than one indication is selected, including indications not under evaluation. These tests would be considered inappropriate even though they could be appropriate according to one of the other indications not being evaluated.

The analyses will be performed on all patients from all physicians according to their allocated group.

Appropriateness for each study indication separately will be performed as a secondary analysis. In this analysis we will include the number of additional indications for the panel as a factor in the analysis.

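### CPOE experience, the planned stratifier and suspected effect modifier, was replaced by laboratory without being recorded as a departure, and no model, adjusted analysis or subgroup uses it

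*SAP*

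**What the plan says.** On the stratifier, the two documents differ.

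- Protocol 8.3: "PCP's will be randomized to either the intervention or control arm after stratification based on their experience in the use of a CPOE". The reason follows: "We suspect that previous experience in using a CPOE will influence the effectiveness of order sets".
- SAP 3.2: "We stratified the randomisation according to the laboratory with which they collaborated (3 strata"). The justification is: "The level of confidence in using a CPOE was associated with the laboratory with which the PCP collaborated". The SAP adds that this spread each laboratory's practices evenly over the arms. It then refers back: "Further details on the randomisation scheme can be found in the protocol under 8.3".

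On data and analysis:

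- Protocol 8.6 lists among the baseline items: "Experience in the use of a CPOE prior to the study".
- Protocol 9.3.2, primary model: "The logistic GEE model will include the allocated group as a factor and patients as the clustering variable".
- SAP 10.2.1, primary model: "The logistic GEE model will include the allocated group and laboratory as factors and PCP as the clustering variable". The diagnostic-error and test-volume models in SAP 10.2.2 carry the same two factors, and SAP 10.2.3 applies the volume method to cascades.
- Protocol 9.4 plans subgroups by indication, plus an analysis limited to patients with study indications only. Protocol 9.5 adjusts for test volume, number of patients, and physician age or years worked. The per-indication analysis in SAP 10.2.1 adds only the number of further indications.

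**The concern.** The trial deliberately mixes physicians who are new to a CPOE with established users (Protocol 4, 5.4, 7.1 and 7.2). The protocol singled out this difference as likely to change the intervention effect and proposed to control it by stratification. The stratifier was then changed, and nothing in the analysis took its place.

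Three things are at stake:

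- **Record.** The two documents name different stratifiers, and the SAP's cross-reference leads to the scheme it did not use. The SAP does not say that it departs from the protocol.
- **Balance and precision.** With 72 practices, a factor that is not stratified on can differ noticeably between arms by chance. Laboratory covers it only as far as laboratory predicts experience.
- **Effect modification.** A main effect for laboratory cannot show whether order sets work differently in new and established CPOE users. If that question is first asked after unblinding, the answer is post hoc.

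**Working it through.** The plan states no figure that depends on this point, so there is nothing to reproduce. The first part compares texts. The second illustrates the possible imbalance under stated assumptions.

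**1. Where CPOE experience appears**

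| Place | CPOE experience used? |
|---|---|
| Protocol 8.3, stratification | Yes, as planned stratifier |
| Protocol 8.6, baseline data | Yes, to be collected |
| Protocol 9.3 models | No |
| Protocol 9.4 subgroups | No |
| Protocol 9.5 adjusted analyses | No |
| SAP 3.2, stratification used | No; laboratory, 3 strata |
| SAP 6.1, database description | Not listed |
| SAP 10.2.1 to 10.2.3 models and additional analyses | No; arm and laboratory, plus number of further indications in the per-indication analysis |

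The SAP's link between laboratory and CPOE use concerns confidence, whereas the protocol's factor is experience.

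**2. Possible chance imbalance**

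Inputs: 72 practices and 280 physicians (SAP 3.2). Assumptions: a 36:36 split; each practice counts as wholly experienced or wholly naive; 24 practices per laboratory, split 12:12. The documents give no experienced share for trial practices. The 30% in Protocol 4 describes all physicians collaborating with the laboratories, so a range is used.

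*Laboratory explains nothing.* With K experienced practices of 72, the number X in one arm is hypergeometric and the between-arm difference in shares is d = (2X − K)/36. Then

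SD(d) = (2/36) × √[36 × (K/72) × (1 − K/72) × 36/71].

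| Share | K | SD of d (percentage points) |
|---|---|---|
| 10% | 7 | 7.0 |
| 20% | 14 | 9.4 |
| 30% | 22 | 10.9 |
| 50% | 36 | 11.9 |

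*Stratified by laboratory, about 30% experienced overall (21 of 72).* With K_j experienced practices of 24 in laboratory j,

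SD(d) = (2/36) × √[Σ 12 × (K_j/24) × (1 − K_j/24) × 12/23].

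| Shares by laboratory | K_j | SD of d (percentage points) |
|---|---|---|
| 30/30/30% | 7, 7, 7 | 10.9 |
| 10/30/50% | 2, 7, 12 | 10.1 |
| 0/10/80% | 0, 2, 19 | 6.8 |

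If laboratory fully determined experience, the SD would be 0. A moderate association therefore removes little of the imbalance, and only a near-deterministic one removes most of it.

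*Experience varying within practices.* Practices average 280/72 = 3.9 physicians. At the other extreme, if physicians' experience were independent within equal-sized practices, 140 physicians per arm at 30% would give SD = √(0.3 × 0.7 × 2/140) = 0.055, or 5.5 points. The practice-level figures are therefore the upper end.

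**The case against.** The best defence is that the change was explained and partly carried through. The SAP gives a reason for using laboratory, this stratifier also balances each laboratory across arms, and laboratory is in all the main SAP models. The analysis therefore matches the randomisation actually done. Chance imbalance on another factor is not bias, and practice-clustered standard errors reflect between-practice variation. No objective asks for an effect by experience. All of this stands. It does not resolve the conflict over the stratifier, and it does not make laboratory a test of effect modification.

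A version difference is also possible. The SAP elaborates protocol version 3.6 of 07/08/2019, and the protocol text available here does not show its version number. If section 8.3 of version 3.6 already describes laboratory strata, the cross-reference is sound and only a note of the change is missing.

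A reader might go further in two ways that the documents do not support:

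- **That experience was dropped from the analysis.** It was never in the protocol's models, subgroups or adjusted analyses. Only the stratifier changed.
- **That the estimate could move by 1 to 2 points, to be set against the detectable 4.1 points in Protocol 9.1.3.** One gets there from 1.96 × √(0.3 × 0.7 × 2/36) = 21.2 points of imbalance times an outcome difference of 5 to 10 points, giving 1.1 to 2.1. No document supports that outcome difference, the 30% is not a trial figure, and whole-practice experience is the extreme case. The protocol's suspicion also concerns the intervention effect. Under pure effect modification only the intervention arm's mix matters, which halves the result to about 0.5 to 1.1. Finally, the 4.1 figure already allows for clustering through a design effect of 12.465, and it assumes 300 physicians at 2.35 per practice.

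**Conclusion.** The point holds as a documentation conflict and a missed use of a planned baseline factor. The stratifier changed from CPOE experience to laboratory without being recorded as a departure, and a suspected effect modifier has no place in any analysis. Type I error is not threatened and the treatment comparison is not biased by the change.

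The size of the loss cannot be determined. If 10 to 30% of practices were experienced and laboratory explained none of it, the SD of the between-arm imbalance would be about 7 to 11 points. This assumes a 36:36 split and practices that are all one or the other, and it shrinks if experience varies within practices or is tied to laboratory. The effect on the treatment estimate cannot be derived from the documents. The conclusion rests on the texts and does not depend on that illustration. The laboratory proxy cannot be called weak or strong, because its association with CPOE use is not quantified.

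**What to change.** Before unblinding, which SAP 8 places after database lock:

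1. **SAP 3.2.** Record the change of stratifier as a dated departure from Protocol 8.3, with its reason, and correct the cross-reference. Do not rewrite Protocol 8.3 retrospectively, because that would hide the departure.
2. **SAP 10.2.1 and 10.2.2.** Add baseline CPOE experience next to laboratory. First confirm that the variable is held and can be linked to the physicians, since SAP 6.1 does not list it and SAP 6.4.1 recodes physician identifiers. Define its scale (binary or graded) and its level (physician or practice). If it is used at practice level, state how several physicians' self-reports become one value.
3. **SAP 10.2.1.** Pre-specify one arm-by-experience analysis of appropriateness, labelled exploratory.

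The cost is SAP wording, a data check, and one extra parameter (if experience is binary) in the adjusted models with 72 clusters. The interaction estimate will be imprecise and should be reported as such. If the variable proves not to be available, item 1 still applies, and the SAP should state that items 2 and 3 could not be done.

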3.3. Sample size

For sample size calculations, we refer to the protocol and appendix 3 of the protocol. At the end of the six-month intervention period the planned sample size was verified based on the number of recruited physicians and the average number of patients per physician. With 280 study physicians (clusters), a sample of 12740 patients (45.5 patients on average per physician) would be necessary to have at least 80% power for the secondary outcome (diagnostic error), assuming the original intra-cluster correlation and diagnostic error rates. At that point we had recruited 11200 patients and it was deemed unfeasible to recruit an additional 1500 patients. Since most recruitments were realised by physicians who had already recruited 50 or more patients, the Steering Committee agreed that attempts to recruit additional patients should target physicians with a low number of recruited patients. Therefore, only those physicians who had not yet recruited 10 patients were allowed another month to recruit additional patients. Specific calculations regarding the sample size and the assumed intra-cluster correlations can be found in the protocol under 9.1.

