To our knowledge there are no sound statistics on the percentage missed diagnoses due to laboratory testing in primary care. Panesar et al (Panesar 2016) estimated that two to three per hundred consultations in primary care result in safety incidents. Between 4 and 45% of these safety incidents may be related to misdiagnosis or missed diagnoses. Assuming 2.5% missed diagnoses in primary care, we calculated that the trial, with an 80% power to detect a non-inferiority of a 1% difference using a significance level of 5%, would need 6032 patients in total. Previous studies have illustrated that in primary care ICCs for clinical outcomes are lower than those for process outcomes and the ICC for adverse effects to be around 0.025 (Adams 2004). Although this may not seem correct, the chances that a physician consistently misses the same diagnosis is less probable than consistently ordering the same test for the same indication. A missed or delayed diagnosis will more probably lead to a change in practice than over- or underutilization of a laboratory test. For this outcome, the unit of analysis will be individual patients and not individual tests as for appropriateness. Therefore, there is one level of clustering less to account for. Assuming a 3 month period in which laboratory tests are ordered for 42 patients, we would need to recruit 290 physicians. In the case of a 6 month period, implying 84 patients for which a laboratory panel is requested, we would need to recruit 220 physicians. For this clinical outcome we will not account for clustering on the level of the PCP as there is no evidence that this influences the amount missed diagnoses by individual physicians. Intuitively, there is no reason to assume that two physicians working together in the same practice would have a greater probability of missing the same diagnosis. Because we believe this outcome to be important in convincing physicians in the widespread use of order sets for laboratory tests, we have chosen to power our study to include this outcome. Figure 16 summarises all the sample size calculations for the outcome 'missed or delayed diagnoses' and their assumptions.

Sample size for comparison of 2 proportions (binary values): non-inferiority trial  
 Missed diagnoses: pA: 2.5%  
 Missed diagnoses: pA: 2.5%  
 Clinically significant change of 1%  
 $\alpha = 0.05$   
 $1-\beta = 0.80$   
 $K = 1$   
 Sample size: 6032  

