3.1. Trial design

Our trial is designed as a cluster randomised controlled trial and powered as a superiority trial for our primary outcome. For the secondary outcome, the trial is designed to establish non-inferiority. The trial will have sufficient statistical power for both outcomes and consists of a six-month intervention period and a six-month follow-up period. The trial design with time points can be found in the protocol under 6.

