6.3. Data cleaning

6.3.1. Inclusion and exclusion criteria

Despite stringent inclusion and exclusion criteria, some patients included in the study do not conform to these predefined criteria. All patients included who are younger than 18 years of age at the start of the study will be excluded from the database. Patients included after 01/06/2018 will be excluded. If a patient had been included at a previous date, laboratory panels included after 01/06/2018 will be excluded. The only exception to this criterium are patients included by physicians who had not included 10 patients on 01/06/2018. They were offered the opportunity to include additional patients throughout June 2018. All patients or laboratory panels included after 01/07/2018 will be excluded.

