7.1. Pre-analysis checks

Prior to database lock, based on the data cleaning actions, a final set of patients who meet the inclusion criteria and for whom tests were ordered for one or more of the study indications will be defined. When the last data collection has been completed and when completed data collections forms for at least 85% of the included patients have been imported into the database, a pre-analysis report will be drafted. This document will report on the status of all databases, including:

- Overview of missing forms per physician
- Overview of missing forms per laboratory
- Overview of missing forms per EHR system

If certain outstanding forms are deemed critical for database lock, the investigators responsible for these forms will be contacted to resolve these issues. The outstanding issues and the timeline for these issues will be reported on the pre-analysis report and signed off by the Chief Investigator, Trial Coordinator and Chief Statistician.

Upon resolution of outstanding actions, the database can be locked.

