10.2.2. Secondary outcome analysis

Diagnostic error

The proportion of patients with a missed diagnosis will be analysed by means of a logistic GEE model that includes allocated group and laboratory as factors and uses PCP as the clustering variable. An independent working correlation matrix will be used. The proportion of patients with a missed diagnosis and associated 95% confidence intervals will be estimated from the model.

The difference in proportions will be obtained by subtracting the two proportions. The associated standard error will be calculated from the rules for the variance of a difference between two independent estimates. The 95% confidence interval for the difference will be calculated.

The non-inferiority limit for missed diagnoses is 1%, i.e. the intervention will be deemed non-inferior if the difference between the allocated groups (intervention – control) is less than 1%. Therefore, the intervention will be deemed non-inferior if the upper limit of the 95% confidence interval lies below 1.

As for the primary endpoint, the analysis will be performed for all 17 study indications together. An additional analysis will be performed that only includes patients who have no indications in addition to the 17 study indications

Test volume

The total number of tests will be analysed using a GEE model for count data (Poisson or Negative Binomial to handle potential overdispersion) that includes allocated group and laboratory as factors in the model and PCP as clustering variable. No offset will be used. The number of tests per patient for each group will be estimated from the model and presented together with their associated 95%

confidence intervals. The effect of the intervention will be presented as the ratio between the two numbers with its 95% confidence interval. Statistical significance will be assessed at a significance level of 5%.

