10.3. Missing data

For about 15% of patients included in the study, no eForm is available (preliminary figures). This measure of missing data is due to technical difficulties in the pseudonymized data collection. No methods for data imputation are foreseen. Patients for whom no data was collected will be excluded from the data analysis. The exact measure of missing data will be reported in the final report.

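### SAP 3.1 claims sufficient power for diagnostic error, but SAP 3.3 and 10.3 leave fewer patients than the SAP requires for 80%, and no power is restated

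*SAP*

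**What the plan says.** - **SAP 3.1, Trial design:** "The trial will have sufficient statistical power for both outcomes and consists of a six-month intervention period and a six-month follow-up period".
- **SAP 3.3, Sample size:** "With 280 study physicians (clusters), a sample of 12740 patients (45.5 patients on average per physician) would be necessary" for at least 80% power on diagnostic error, keeping the original intra-cluster correlation and error rate. Then: "At that point we had recruited 11200 patients and it was deemed unfeasible to recruit an additional 1500 patients". Only physicians with fewer than 10 patients received one more month. SAP 6.3.1 confirms this: "They were offered the opportunity to include additional patients throughout June 2018". The yield of that month is not given.
- **SAP 10.3, Missing data:** about 15% of patients have no eForm (a preliminary figure), nothing is imputed, and patients without data leave the analysis. SAP 7.1 starts the pre-analysis report "when completed data collections forms for at least 85% of the included patients have been imported into the database". SAP 6.3.3 also drops eForms that cannot be linked to a laboratory panel, without giving a number.
- **SAP 10.2.2, decision rule:** "the intervention will be deemed non-inferior if the upper limit of the 95% confidence interval lies below 1", meaning 1 percentage point. The GEE model clusters on primary care practice (PCP).
- **Protocol 9.1.2 and Figure 16:** 6032 patients before clustering, from a 2.5% error rate in both arms, a 1-point margin, 80% power and a 5% significance level. The design effect uses a physician-level ICC of 0.025. Practice-level clustering is deliberately left out.

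No section of either document gives the final number recruited, the number expected in the analysis, or the power at that number.

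**The concern.** SAP 3.1 and 3.3 cannot both stand. One claims sufficient power for both outcomes. The other gives the number needed for 80% and says it was not reached and could not be, and SAP 10.3 then removes more patients.

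The protocol says it sized the trial for this outcome because showing no increase in missed diagnoses matters for persuading physicians to adopt order sets. A confidence interval that spans the margin would therefore be read against a power claim that no longer applies, and the expected precision is not on record before the analysis.

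Two features of the re-check make the position less favourable than the patient count alone suggests. The alpha behind 6032 may not match the decision rule, and the re-check treats 280 physicians as the clusters although 72 practices were randomised and the model clusters on practice.

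**Working it through.** **Inputs.** Error rate p = 2.5% in both arms, margin 1 point, 80% power, 1:1 allocation, physician ICC 0.025 (Protocol 9.1.2, Figure 16). 280 physicians in 72 PCPs (SAP 3.2). Required 12,740 and recruited 11,200 (SAP 3.3). Loss of 15% (SAP 10.3).

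**Step 1: reproduce the SAP's figure.**
- Total N before clustering = 2 × (z_α + z_0.80)² × 2p(1−p) / 0.01². One-sided 5% gives 6,028 (document: 6032). One-sided 2.5% gives 7,653, which does not match. So 6032 rests on one-sided 5%.
- DE = 1 + 0.025 × (45.5 − 1) = 2.1125, and 6032 × 2.1125 = 12,743. The 12,740 is correct on its assumptions.

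**Step 2: power at the numbers available.** Power = Φ(0.01/SE − z_α), with SE = √[2p(1−p)/(Neff/2)], Neff = N/DE and DE = 1 + 0.025 × (N/280 − 1).

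| Patients | Per physician | DE | Neff | Power, one-sided 5% | Power, 95% CI read as two-sided |
|---|---|---|---|---|---|
| 12,740 (required) | 45.5 | 2.1125 | 6,031 | 80.0% | 70.1% |
| 11,200 (at the check) | 40 | 1.975 | 5,671 | 77.8% | 67.4% |
| 10,829 (12,740 less 15%) | 38.7 | 1.942 | 5,577 | 77.2% | 66.7% |
| 9,520 (11,200 less 15%) | 34 | 1.825 | 5,216 | 74.8% | 63.8% |

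**Step 3: does the unknown final N matter?** To keep 12,740 after 15% loss, 12,740/0.85 ≈ 14,990 must be recruited, about 3,790 more than 11,200. The SAP called 1,500 more unfeasible. Had the extra month closed the whole gap, 10,829 would remain. The direction therefore does not depend on the missing count.

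**Step 4: sensitivity to the error rate and to practice-level correlation (9,520 patients).** The documents give no correlation between physicians of one practice for this outcome, so the non-zero values of ρ_b are assumptions. DE = 1 + 0.025 × (34 − 1) + ρ_b × (132.2 − 34), where 132.2 = 9,520/72. Cells show power at one-sided 5% / under the two-sided 95% CI rule.

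| ρ_b | DE | Neff | Rate 1.5% | Rate 2.0% | Rate 2.5% |
|---|---|---|---|---|---|
| 0 (protocol) | 1.825 | 5,216 | 90.8% / 84.4% | 82.5% / 73.2% | 74.8% / 63.8% |
| 0.005 | 2.316 | 4,110 | 83.9% / 75.1% | 74.0% / 62.9% | 65.8% / 53.7% |
| 0.01 | 2.807 | 3,391 | 77.4% / 66.8% | 66.8% / 54.8% | 58.7% / 46.2% |
| 0.025 | 4.281 | 2,224 | 61.6% / 49.2% | 51.6% / 39.1% | 44.6% / 32.6% |

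At ρ_b = 0 the choice of cluster changes nothing, and 80% is reached at an error rate of about 2.16% or lower (one-sided 5%) or about 1.69% or lower (two-sided 95% CI). Across the table the expected 95% CI half-width (1.96 × SE) runs from 0.66 points (1.5%, ρ_b = 0) to 1.30 points (2.5%, ρ_b = 0.025).

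**The case against.** **The shortfall is disclosed, and 3.1 looks like carried-over design language.** Protocol section 6 makes the same claim. SAP 3.3, in the same chapter as 3.1, reports the required number, the number reached and the Steering Committee's decision, and SAP 10.3 promises the exact missing fraction in the final report. This limits the harm but does not make the sentence true. SAP 6.3.1 admits no patient after 01/07/2018, and the SAP cites a protocol version dated 2019, so recruitment had closed before the text was written.

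**The loss is small on the SAP's own terms.** This stands: 2 to 5 points at one-sided 5%. The larger reductions come from the alpha and clustering questions. Neither is caused by the shortfall; the alpha gap exists even at 12,740. They belong here only because a restated power must settle both.

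**The practice-level values are assumed.** This also stands. The protocol argues openly for zero, the GEE accounts for practice in the analysis, and 0.025 is a boundary case in which patients of different physicians in a practice correlate as strongly as those of one physician. The result also depends on the model: a single practice-level ICC of 0.005, replacing the physician ICC instead of being added to it, gives 78.3% with 9,520 patients at one-sided 5%.

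**The true error rate may be lower.** Protocol 9.1.2 cites 2 to 3 safety incidents per 100 consultations, 4 to 45% of them linked to misdiagnosis or missed diagnosis. That multiplies to about 0.08% to 1.35%. These are per consultation, not per patient over six months, so they are only indicative. At 1.35%, 9,520 patients and ρ_b = 0, power is 93.1% / 87.9%. The claim in 3.1 therefore fails at the planning rate of 2.5%, not at every rate the protocol mentions.

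**The analysed number is unknown.** Outstanding forms may still arrive, so 9,520 is a scenario. Step 3 shows that the direction holds.

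**Conclusion.** The concern holds and should be fixed. At the planning rate, and with the SAP's own ICC and alpha, power for diagnostic error is about 75 to 78%, not the 80% the trial was sized for. If the 95% confidence interval is two-sided, it is about 64 to 67%, and 12,740 patients would not have been enough either.

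These figures assume a 2.5% rate in both arms, equal patient numbers per physician, no correlation between physicians of one practice, and a 15% loss applied to 11,200. They are not upper bounds, since a lower error rate or better form retrieval raises power. Practice-level correlation lowers it, and so does uneven recruitment, which SAP 3.3 describes: with an assumed coefficient of variation of 0.5 to 1.0 in patients per physician, power with 9,520 patients at one-sided 5% falls to 71% to 60%.

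The confidence interval will still show whether the margin is excluded, so the result stays readable. The defect is an outdated power claim with no stated expectation of precision to replace it.

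**What to change.** - **SAP 3.1:** remove or qualify the power claim for diagnostic error and refer to 3.3.
- **SAP 3.3:** give the final number recruited and the number expected in the analysis. Restate power or expected confidence-interval half-width with 72 PCPs as clusters and an alpha that matches the decision rule. A short table over practice-level ICC (for example 0, 0.005, 0.01, 0.025) and error rate (1.5%, 2.0%, 2.5%) is enough. If the final analysable number is not yet fixed, show a range.
- **SAP 10.2.2:** state whether the 95% confidence interval is two-sided.
- **Optional:** say that an interval containing 1 percentage point will be reported as inconclusive, and report the observed practice-level ICC.

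The cost is one or two sentences and a small table, with a less favourable stated power. No extra patients and no change to the model are needed.
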